Several outside/environmental factors can affect a patient's surveillance frequency. In our preliminary analysis using the US population-based Surveillance, Epidemiology and End Results (SEER)-Medicare dataset, we found race, marital status, and regional socioeconomic determinants (high school graduation rate) to be associated with different PSA surveillance frequencies. The NCDB captures a comprehensive list of covariates (see above). We will examine if surveillance frequency is associated with each individual factor and account for these factors using modeling as above. Finally, we recognize that there may still be important unmeasured confounders in our study; therefore, we plan to use sensitivity analyses to estimate the impact of a hypothetical unmeasured/unobserved confounder, using similar methodology used in a prior study by the co-I ([name]).²² This analysis will allow us to determine the extent of confounding that would substantively change our study findings.

A conceptual diagram (directed acyclic graph) demonstrating the relationship between measured covariates and our selected study outcomes for Aim 1 is provided in Figure 2 below.

Figure 2. Directed Acyclic Graph for the Hypothesized Relationship between Selected Study Variables and Outcomes for Aim 1

Footnote: Analyses will be stratified by the type of initial treatment (surgery, radiation) and recurrence risk (low, intermediate, high) and the hypothesized relationships may vary somewhat by each clinical scenario. Relationship between variables identified as pertaining to Aim 2 are noted in Figure 3.

Statistical power: There are >1,400 CoC-accredited hospitals. With 10 patients sampled at each hospital, we expect 14,000 patients will be available for analysis. We will intentionally sample approximately the same number of patients in each of the 6 cohorts (risk group x primary treatment), providing 2,333 patients in each cohort. Within each cohort, patients receiving different surveillance frequencies will be compared. Based on preliminary analysis of SEER-Medicare data, the national patterns of PSA surveillance in the first year are: (Table 2)

Number of PSAs	Low Risk	Intermediate Risk	High Risk
1	20%	18%	17%
2-3	61%	59%	53%
4	19%	23%	30%

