We have proposed using multivariable modified Poisson/binomial regression models and adjusted Cox Proportional Hazards models as our primary analytic approach. Although estimates from multivariate models have been shown to be similar to those using propensity score methods,³⁸ we plan to conduct propensity score matched and weighted sensitivity analyses for all outcomes in an attempt to address potential residual confounding. For propensity score analyses, we will use logistic regression to estimate the probability of being in each of the surveillance groups as a function of measured patient and hospital characteristics in an attempt to achieve balance on measured characteristics and to obtain unbiased estimates of the treatment effect under the assumption of no unmeasured confounding.^{39,40} Variables that will be included in the propensity score are those that are predictors of the outcome of interest or confounders of the treatment (surveillance frequency) and the outcome.⁴¹ Separate propensity score models will be used for each outcome of interest and modified based on theoretical relationships between the measured variables and the specified model outcome. We will use both propensity score weighting and matching as the application method may provide insight into treatment effect heterogeneity.⁴²

1) Propensity score weights: We will examine the distribution of propensity scores across groups and trim observations from the non-overlapping ends of the distribution if necessary.⁴³ We will create inverse probability of treatment weights (IPTW) and stabilize these weights to reflect the sample size of each group. The IPTW will be used in Aims 1 and 2 to balance the measured characteristics between the comparison groups.

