2) Propensity score matching is another approach to balance sample characteristics,⁴⁴ and will be explored as an additional sensitivity analysis [IR-5]. Matching provides an intuitive way to evaluate the extent to which the surveillance groups overlap with one another and automatically excludes individuals who do not have a similar (matching) individual available. This method provides an estimate of the effect among individuals who would have been candidates for any of the three surveillance methods. Individuals who are unmatched can then be evaluated to determine if specific patient characteristics drive surveillance frequency. After we obtain propensity scores for each individual using the methods described above, matching can be conducted using a “greedy algorithm”⁴⁴ across comparison groups to ensure good overlap among groups.

3) Assessment of sample balance: To ensure balance of sample characteristics, we will test for differences among comparison groups in the mean (for continuous variables) or distribution (for categorical variables) of each covariate using t-tests and chi-squared/Fisher’s exact tests, respectively, both before and after applying the generated propensity score weights. In addition, for the propensity score matched sample, we will assess the balance of study covariates using standardized differences across comparison groups. If there is residual

imbalance after propensity score weighting or matching, we will include unbalanced variables in the outcome model to ensure proper control of these confounding factors.

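### If matching uses a fixed ratio without replacement, many unmatched men are merely surplus to the ratio, so they cannot show poor overlap or what drives surveillance frequency

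*Combined protocol and SAP*

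**What the plan says.** In section C3 (Avoidance of bias), item 2, matching is a further sensitivity analysis, and "matching can be conducted using a “greedy algorithm" across the comparison groups. The ratio, replacement rule, caliper and matching order are not given. The item offers matching as a way to see how far the groups overlap and says that it "automatically excludes individuals who do not have a similar (matching) individual available". On the target population it says: "This method provides an estimate of the effect among individuals who would have been candidates for any of the three surveillance methods". It then proposes a use for the men left out: "Individuals who are unmatched can then be evaluated to determine if specific patient characteristics drive surveillance frequency".

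The group sizes come from Aim 1, Statistical power. The plan expects 14,000 patients, "providing 2,333 patients in each cohort", one cohort for each combination of risk group and treatment. Table 2 gives the shares with 1, 2-3 and 4 PSA tests in the first year: 20/61/19% (low risk), 18/59/23% (intermediate) and 17/53/30% (high). The shares come from SEER-Medicare and are given by risk group, not by treatment.

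**The concern.** The plan gives unmatched status one meaning: no similar man was available. In fixed-ratio matching without replacement there is a second route. A man can have many close counterparts and still be left out because they are all used up. When one group holds 53-61% of the cohort and the smallest holds 17-19%, the second route can dominate.

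Two readings are then at stake. A high unmatched count would be taken as poor overlap where overlap is good. A comparison of unmatched with matched men would be taken to show what drives surveillance frequency, although it depends heavily on which groups have a surplus.

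**Working it through.** **Inputs.** Cohort size and shares are from Aim 1, Statistical power. The plan's own figure reproduces: 14,000 / 6 = 2,333. Assumptions: matching uses a fixed ratio 1:r:1 without replacement, with r men from the 2-3-test group per set. The Table 2 shares hold in both treatment cohorts. The row labelled 4 stands for the group with 4 or more tests.

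**Step 1: loss forced by group size.** The number of matched sets, as a share of the cohort, is at most m = min(p1, p4, p2-3 / r). The unmatched share is therefore at least 1 - (2 + r) x m.

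| Risk | 1:1:1 | 1:2:1 | 1:3:1 |
|---|---|---|---|
| Low (m = 0.19) | 1 - 3(0.19) = 43% | 1 - 4(0.19) = 24% | 1 - 5(0.19) = 5% |
| Intermediate (m = 0.18) | 1 - 3(0.18) = 46% | 1 - 4(0.18) = 28% | 1 - 5(0.18) = 10% |
| High (m = 0.17) | 1 - 3(0.17) = 49% | 1 - 4(0.17) = 32% | 1 - 5(0.17) = 15% |

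Under 1:1:1 this is about 1,003, 1,073 and 1,143 of 2,333 men. These are floors, since a caliper can only add to them. With replacement or a variable ratio, group size forces no loss.

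**Step 2: who the surplus men are.** Under 1:1:1 the 2-3-test group loses 61 - 19 = 42, 59 - 18 = 41 and 53 - 17 = 36 percentage points of the cohort. That is 42/61 = 69%, 41/59 = 69% and 36/53 = 68% of that group. It supplies 42/43 = 98%, 41/46 = 89% and 36/49 = 73% of the size-forced unmatched. Under 1:2:1 it still supplies most of them: 23/24, 23/28 and 19/32. Under 1:3:1 this no longer holds everywhere. In high risk, 13 of the 15 points come from the group with 4 or more tests (30 - 17 = 13). So the ratio also decides which men are left over.

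**Step 3: does unmatched mean no comparator?** A simulation of greedy 1:1:1 matching used one normal score, an assumed caliper of 0.2 SD and 30 runs per risk group.

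- No covariate difference between groups: 46-49% were unmatched, and only about 1% of those lacked a man within the caliper in another group.
- Means shifted by 0.3 SD per group (0.6 SD between the extreme groups): 53-56% were unmatched, and about 1.6% of those lacked a comparator.
- Simulations with other covariate structures found that 91-97% of unmatched men had a comparator in both other groups.

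**Step 4: does the unmatched set reveal a driver?** In the shifted simulation the score is a true driver of equal strength in all three risk groups. The unmatched-minus-matched mean difference was -0.045 SD (low), 0.192 SD (intermediate) and 0.388 SD (high). In low risk the driver almost vanishes: the surplus is nearly all from the middle group, whose mean lies between the other two. In high risk it shows, because the group with 4 or more tests also has a surplus. One driver gives three answers, and what changes between them is the group sizes.

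**The case against.** The case on the other side is substantial, and most of it stands.

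- **The ratio is unstated.** A reader might infer that about half of each cohort will be discarded. The documents do not support that as a fact about the plan. It needs 1:1:1 without replacement, and the loss ranges down to 5-15% under 1:3:1 and to none with replacement or a variable ratio. With those last two, the plan's account of exclusion is essentially right.
- **Sound checks are already planned.** C3, item 1, will examine propensity score distributions across groups and trim non-overlapping ends. Aim 1 will test each factor's association with surveillance frequency. The propensity model itself relates group membership to patient and hospital characteristics. None of these relies on unmatched men.
- **The sentence is permissive.** It says what can be done and sets no inference rule. Where the groups did not differ, unmatched and matched men differed by no more than 0.01 SD, so surplus men created no false driver in that simulation. The demonstrated failure is missing a real driver.
- **Precision.** The size cap costs little for 1 versus 4 or more tests. The standard error ratio is sqrt[(2/m) / (1/n1 + 1/n4)], with m here the number of matched sets. It is 1.01 for 467 and 443 men (m = 443), 1.06 for 420 and 537 (m = 420) and 1.13 for 397 and 700 (m = 397).
- **Heterogeneity.** C3 uses both weighting and matching, "as the application method may provide insight into treatment effect heterogeneity". A reader might infer that any gap between the two results will be declared effect heterogeneity. The wording is tentative and no such rule is stated.

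What does not fall away is the interpretive step itself. Under any fixed ratio without replacement, unmatched status mixes two kinds of men, and the plan recognises only one.

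**Conclusion.** The point holds as a fault of interpretation in one sensitivity analysis. Given fixed-ratio matching without replacement, and Table 2 shares that apply in both treatment cohorts, group size alone leaves at least 43-49% (1:1:1), 24-32% (1:2:1) or 5-15% (1:3:1) of a cohort unmatched. Under 1:1:1 and 1:2:1 the surplus is mostly from the 2-3-test group. Unmatched status then overstates poor overlap and can hide a real driver of frequency. The simulated results also assume a 0.2-SD caliper and 1:1:1 matching.

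A reader might infer that the study's main findings are at risk. They are not: the primary modified Poisson/binomial and Cox models and the inverse-probability-weighted analysis do not depend on matching. The point deserves correction because the step as written can give a wrong answer and the remedy is nearly free.

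**What to change.** In C3, item 2:

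(a) Judge overlap by propensity score support. State a caliper, and report men with no man of another group within it separately from men surplus to the ratio.

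(b) Take drivers of surveillance frequency from the full-sample propensity model and the factor-by-factor analysis already in Aim 1. Delete the sentence that infers them from unmatched men.

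(c) If matching is kept, state the ratio, replacement rule and caliper, and use a variable ratio or matching with replacement so that comparable 2-3-test men are not discarded. Overlap weights are an optional alternative for the men who were candidates for any of the three frequencies. Replacing matching with them is a preference, not a requirement.

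The cost is a few lines of SAP text, slightly more code and a matched table that is less simple to present. No new data are needed.

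### In the propensity-weighted sensitivity analyses, covariate balance is judged by significance tests whose sensitivity depends on group size, and the result decides which covariates are added to the weighted outcome model

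*Combined protocol and SAP*

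**What the plan says.** C3, Avoidance of bias, item 3 (Assessment of sample balance) sets the rule. For the weighted sample, "we will test for differences among comparison groups in the mean (for continuous variables) or distribution (for categorical variables) of each covariate using t-tests" for continuous variables and chi-squared or Fisher's exact tests for categorical ones, "both before and after applying the generated propensity score weights". A different measure is then added for the other propensity-score method only: "for the propensity score matched sample, we will assess the balance of study covariates using standardized differences across comparison groups". If residual imbalance is found after either method, "we will include unbalanced variables in the outcome model to ensure proper control of these confounding factors".

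Item 3 gives no significance level for these tests, no threshold for the standardized difference, and no rule for combining comparisons across three surveillance groups.

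On scope, the opening of C3 makes multivariable regression and adjusted Cox models the primary approach and describes the propensity-score analyses as sensitivity analyses for all outcomes. Item 1 of C3 states that "The IPTW will be used in Aims 1 and 2 to balance the measured characteristics between the comparison groups".

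**The concern.** A p-value for a baseline difference reflects both the size of the difference and the number of patients. The bias from a covariate depends on the size of its imbalance and its relation to outcome, not on the number of patients. Under the planned rule, the same imbalance would be called unbalanced and adjusted for in a large sample, yet called balanced and left alone in a small one. The small groups (patients with 1 test or with 4 or more) lie at the two ends of the main contrast.

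The sentence about adjusting for unbalanced variables does not remove the problem, because for the weighted sample the test is the only stated way for a variable to count as unbalanced. There is also a problem of comparison: weighted and matched analyses would be held to different balance standards, so a disagreement between them would be harder to interpret. The analyses exist to probe residual confounding, and this check weakens them for that purpose.

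**Working it through.** **Inputs.**
- Aim 1 cohort size, from Aim 1, Statistical power: 1,400 × 10 / 6 = 2,333. Reproduced.
- Aim 2 sample, from Aim 2, Statistical power: 1,079 completers at 12 months; 1,079 × 0.75 = 809 after 25% attrition. Reproduced.
- Group shares (1 / 2–3 / 4 tests), from Table 2: low risk 20/61/19%, intermediate 18/59/23%, high 17/53/30%. The plan's smallest Aim 2 group of 154 is 809 × 0.19, the low-risk column. The other columns give 809 × 0.18 = 146 and 809 × 0.17 = 138.
- Aim 2 strata: the Figure 3 footnote mentions stratification by treatment and risk, hence up to six strata. Equal strata of 809/6 ≈ 135 are an assumption.
- Two-sided 0.05 for the balance tests is an assumption, borrowed from the outcome power statements.

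**Smallest standardized difference that reaches significance** for two groups of n₁ and n₂, ignoring the effect of weighting:

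d_min = 1.96 × √(1/n₁ + 1/n₂)

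The lower end of each range is 2–3 versus 4 or more tests in the high-risk column. The upper end is 1 versus 4 or more tests in the low-risk column.

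| Setting | Lower end | Upper end |
|---|---|---|
| Aim 1 cohort, 2,333 | n = 1,236 and 700: 0.093 | n = 467 and 443: 0.130 |
| Aim 2, N=809 | n = 429 and 243: 0.157 | n = 162 and 154: 0.221 |
| Aim 2, N=1,079 | n = 572 and 324: 0.136 | n = 216 and 205: 0.191 |
| Aim 2 stratum, 809/6 | n = 71 and 40: 0.386 | n = 27 and 26: 0.541 |

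**Chance that a true difference of 0.20 is flagged** (normal approximation, all pairs and columns): 85–99% in an Aim 1 cohort, 43–70% in Aim 2 at N=809, 11–17% in an Aim 2 stratum. For a true difference of 0.10 the first two are 33–56% and 14–24%.

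**Effect of weighting.** Weighting lowers the effective sample size. With an assumed design effect of 1.5, each threshold is multiplied by √1.5 = 1.22. This gives 0.11–0.16 in an Aim 1 cohort, 0.19–0.27 in Aim 2 at N=809 and 0.47–0.66 in a stratum. The documents give no design effect, so this shows direction only.

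**The alternative rule under no true imbalance.** Three group means were simulated as independent normals with variance 1/n, and the maximum pairwise difference was compared with 0.10. It is exceeded for about 18–20% of covariates in an Aim 1 cohort, 53–56% in Aim 2 at N=809 and about 90% in an Aim 2 stratum.

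**The case against.** **The primary results do not depend on this check.** A reader might infer that the test decides which confounders enter the main models. The documents do not support that. C3 makes the weighted analyses sensitivity analyses. Covariates in the primary models are set elsewhere: risk variables as controls under Aim 1's potential problems, and the listed covariates under Aim 2's data analysis. This stands in full and limits the weight of the point.

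**A covariate that passes the test is still in the weights.** C3 selects propensity-score variables as predictors of outcome or confounders, not by p-value, so the rule in item 3 is a second layer of adjustment. A reader might infer that residual confounding in the weighted analyses has been shown. It has not: weighting must first fail for a covariate and the test must then miss it, and nothing in the documents shows either.

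**The numbers rest on assumptions.** The 0.05 level is not stated for these tests. Equal strata are assumed, stratification of Aim 2 appears only in a figure footnote, and Aim 2 power is pooled. Balance could be checked in all 1,079 completers, particularly as item 5 of C3 plans imputation to use the whole sample. Table 2 comes from SEER-Medicare, not from either study sample. The formula is for unweighted independent groups. These are limits on precision; they do not change the ordering, with Aim 2 much worse than Aim 1.

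**A fixed 0.10 cut-off has its own cost.** It flags many covariates by chance in small groups, as shown above. This stands and shapes the fix. That a t-test compares only two groups is minor, since it can be run pairwise.

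**Conclusion.** The concern holds for the weighted sensitivity analyses in both aims. The plan judges balance there by significance tests alone and uses the result to choose added covariates, while already planning a size-independent measure for the matched sample.

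In Aim 1 the effect is slight: the tests flag differences from about 0.09–0.13, close to the usual 0.10 convention, and a true 0.20 is rarely missed before any loss from weighting. In Aim 2 it is material: differences up to about 0.16–0.22 at N=809, or 0.14–0.19 at N=1,079, can pass as balanced, and up to 0.39–0.54 in a stratum if Aim 2 is analysed in six equal strata. The last range is the least secure. The 0.10 benchmark is a convention and appears nowhere in the documents.

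The conclusion is that leftover imbalance could go unnoticed, not that it exists or that any primary estimate is biased. The change is worth making before analysis but is not critical to the main results.

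**What to change.** In C3, item 3, extend standardized differences to the weighted sample. Compute them with the weights applied, take the maximum over the three pairwise comparisons, and state one threshold for weighted and matched samples alike. Use that threshold, not p-values, to judge balance and choose any covariates added to the outcome model. If 0.10 is chosen, say that it is a convention.

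For Aim 2, either apply the threshold to the pooled sample and not within strata, or drop the selection step and adjust the weighted outcome model for the prespecified prognostic covariates. The second option is simpler, because at N=809 about half of covariates would exceed 0.10 by chance even when pooled.

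The cost is small: no new data, no change to the primary models, and a statistic already planned for matching. The price is some extra covariates flagged by chance, which matters little in Aim 1 (about 18–20%) but would make the rule nearly uninformative in an Aim 2 stratum, where the smallest group would have about 23–26 patients.
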